#### **Objectives:**

**Primary:** The primary objective of this study is to assess the safety of single infusions with the RePlasTM FDP product at increasing fixed doses of either 1 unit (approximately 270 mL), 2 units (approximately 540 mL), or 3 units (approximately 810 mL) in normal healthy subjects. In the 2 lower dose cohorts, safety will also be assessed in terms of the type of autologous plasma used as the starting material in the manufacture of the investigational product:

- RePlasTM FDP product manufactured from autologous FFP derived from whole blood (WB) donations where Citrate Phosphate Dextrose (CPD) is the anticoagulant, or RePlasTM FDP-CPD; and
- RePlasTM FDP product manufactured from autologous FFP collected during plasmapheresis where Acid Citrate Dextrose (ACD) is the anticoagulant, or RePlasTM FDP-ACD.

The highest dose cohort will receive FDP manufactured only from FFP collected by plasmapheresis (FDP-ACD). Conclusions on whether the study meets its safety objectives will be based only on treatment emergent adverse events (TEAEs). TEAEs are adverse events (AEs) that occur after administration of the study treatment, plasma infusion, has begun. AEs occurring prior to treatment (e.g., AEs that occur during autologous plasma collection) will not be considered relevant to the study's objectives.

Secondary: The secondary objectives are to:

Assess the safety of a fixed-dose infusion of 3 FDP units (approximately 810 mL) in
comparison to infusion with the same dose of autologous FFP collected during
plasmapheresis; and

Determine if the changes in specific coagulation factors, hematology, and chemistry values
are similar within clinically meaningful levels after infusion of either 3 units of autologous
FDP or FFP.

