The timeframe for the collection of AEs will begin at plasma collection and will continue through 7 days after the last required sample collection (Day 29). Any AE, regardless of its relationship to study product, will be recorded in the AE section of the eCRF. However, any AE that occurs after the informed consent is signed, but before the first infusion visit, will be recorded as medical history, unless it is related to a study procedure. AEs associated with a study procedure (eg, blood or plasma donation) will be recorded in the AE section of the eCRF.

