4.2.2 Safety Populations

The three subject populations for assessing safety are defined as those who:

- Receive any volume of infused product; (i.e., In Cohort 3 subjects this includes those who received a partial dose at either Infusion Visit) (**S1**);
- Receive the full infusion dose and have at least one outcome measure (**S2**); and
- Receive the full infusion dose and can be fully evaluated because in: (**S3**, or the per protocol population).
 - Cohorts 1 and 2 the subjects also minimally completed the 7-day follow-up visit; and

- Cohort 3 the subjects had both complete infusion doses and minimally completed the 7-day follow-up visit after the second infusion.

The demographic tables (Table 1.1- Table 1.20) will include all five analysis populations listed in Section 4.2 unless it is found that both full populations include the same subjects, in which case only one table for the F1 and F2 population will be produced with the title indicating that it represents the F1, F2 populations, unless otherwise specified. Likewise, if all three safety populations are found to include the same subjects, only one table will be produced with the title indicating that it represents all safety populations, the S1, S2 and S3, unless otherwise specified. This pattern of table reduction will be repeated for the remaining tables unless otherwise indicated. Subject disposition tables will include all five populations. AE tables that display overall AE incidence will include all five populations. Tables that are restricted to TEAEs will include the safety populations only. Study drug exposure will be presented in the first safety population (S1). All other analyses will be performed in the third safety population only (S3).

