4.5.3.1 Primary Safety Endpoints

The primary safety endpoints to be assessed are AEs, specifically:

- TEAEs;
- SAEs;
- SUSARs; and
- Deaths.

Descriptive statistics will be used to analyze the primary safety endpoints. Tables produced to exhibit the primary safety endpoint data will be presented by the specific type of plasma product infused. In Cohorts 1 and 2, this data will be presented by FDP product type, FDP-ACD and FDP-CPD; in Cohort 3 by experimental product and control product, FDP and FFP. The primary safety data reported to the DSMB for Cohort 3 will be masked. Unblinding during the study will only occur in accordance with Section 3.3.2 following Westat's SOP DA-504 Development of a Plan for Randomization, Masking, and Unmasking.

In general, AEs that occur in Cohort 3 subjects within 14 days after infusion will be attributed to the most recently infused product. However, there may be exceptions to use of this temporal attribution rule to all transfusion-related AEs given the possibility that those AEs that occur after infusion with the second product may potentially be related to infusion with the first infusion product (e.g., an immunogenic response).

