Special Note: For Cohort 3, there will be an Open and Closed session for the DSMB. For the Open session only Figure 2 will only show overall totals as shown above with the figure number having the word “(Open)” after the figure number before the decimal. Open session Figure 2 will be produced by the blinded statistician. For the Closed session, the treatment arms will be masked as A and B as shown above. The figure number will have the word “(Closed)” after the figure number before the decimal. Closed session Figure 2 will be produced by the unblinded statistician. Final data analysis for Cohort 3 will use the labels FDP-ACDxFFP and FFPxFDP-ACD for the treatments after the study is unblinded and the word “(Closed)” will be removed from the figure number.

Table 2.1. - Table 2.15. Overview of Subject Incidence of Adverse Events (AEs)

Subject Incidence of AEs – Cohort 1 (270 mL)

Full Analysis Population – F1 (N=XX)

**FDP-1
 Phase I**

	FDP-CPD (N=XX) n (% ^a)	FDP-ACD (N=XX) n (% ^a)
Adverse Events	xx (xx.x)	xx (xx.x)
Treatment Emergent Adverse Events	xx (xx.x)	xx (xx.x)
Treatment-Emergent Adverse Events Related to Study Treatment	xx (xx.x)	xx (xx.x)
Serious Adverse Events	xx (xx.x)	xx (xx.x)
Adverse Events Leading to Discontinuation of Investigational Product	xx (xx.x)	xx (xx.x)
Fatal Adverse Events	xx (xx.x)	xx (xx.x)

Table 2.1. - Table 2.15 (Open). Overview of Subject Incidence of Adverse Events (AEs)

Subject Incidence of AEs – Cohort 3 (810 mL)

Full Analysis Population – F1 (N=XX)

**FDP-1
 Phase I**

	Total (N=XX) n (% ^a)
Adverse Events	xx (xx.x)
Treatment Emergent Adverse Events	xx (xx.x)
Treatment-Emergent Adverse Events Related to Study Treatment	xx (xx.x)
Serious Adverse Events	xx (xx.x)
Adverse Events Leading to Discontinuation of Investigational Product	xx (xx.x)
Fatal Adverse Events	xx (xx.x)

Notes: Subjects may be counted in more than one row.

^a=Denominator for each % is the treatment group N.

Table 2.1. - Table 2.15 (Closed). Overview of Subject Incidence of Adverse Events (AEs)
Subject Incidence of AEs – Cohort 3 (810 mL)
Full Analysis Population – F1 (N=XX)
FDP-1
Phase I

	A (N=XX) n (% ^a)	B (N=XX) n (% ^a)
Adverse Events	xx (xx.x)	xx (xx.x)
Treatment Emergent Adverse Events	xx (xx.x)	xx (xx.x)
Treatment-Emergent Adverse Events Related to Study Treatment	xx (xx.x)	xx (xx.x)
Serious Adverse Events	xx (xx.x)	xx (xx.x)
Adverse Events Leading to Discontinuation of Investigational Product	xx (xx.x)	xx (xx.x)

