^c=Denominator adjusted because gender-specific event for females: N=XX (A), N=XX (B) [for applicable PTs].

Preferred Terms within System Organ Class are sorted in descending order of frequency based on the TEAE category.

Table 6.X (Open). Summary of TEAEs by Maximum CTCAE Grade
Subject Incidence of TEAEs by Maximum CTCAE Grade – Cohort 3 (810 mL)
Safety Population – S1 (N=XX)
FDP-1
Phase I

Table 6.X (Closed). Summary of TEAEs by Maximum CTCAE Grade
Subject Incidence of TEAEs by Maximum CTCAE Grade – Cohort 3 (810 mL)
Safety Population – S1 (N=XX)
FDP-1
Phase I

Notes: Subjects may be included on more than one row.

^a=Denominator for each % is the treatment group N. Grade 1=Mild, 2=Moderate, 3=Severe, 4=Life-threatening, 5=Fatal.

^b=Denominator adjusted because gender-specific event for males: N=XX (A), N=XX (B) [for applicable PTs].

^c=Denominator adjusted because gender-specific event for females: N=XX (A), N=XX (B) [for applicable PTs].

Preferred Terms within System Organ Class are sorted in descending order of frequency based on the TEAE category.

64

Program Path:

Data extract date:

Data source: ADAE Cross Reference: Listing 13

Table 7.1. - Table 7.3 (Open). Summary of Serious Adverse Events (SAEs)
Subject Incidence of SAEs
Safety Population – S1 (N=XXX)
FDP-1
Phase I

	Cohort 1		Cohort 2		Cohort 3
Preferred Term	FDP-CPD 270 mL (N = XX) n (% ^a)	FDP-ACD 270 mL (N = XX) n (% ^a)	FDP-CPD 540 mL (N = XX) n (% ^a)	FDP-ACD 540 mL (N = XX) n (% ^a)	810 mL (N = XX) n (% ^a)
Number of subjects reporting serious adverse events	xx (xx.x)	xx (xx.x)	xx (xx.x)	xx (xx.x)	xx (xx.x)
	xx (xx.x)	xx (xx.x)	xx (xx.x)	xx (xx.x)	xx (xx.x)
[Preferred Term #1]	xx (xx.x)	xx (xx.x)	xx (xx.x)	xx (xx.x)	xx (xx.x)
[Preferred Term #2] ^{b,c}	xx (xx.x)	xx (xx.x)	xx (xx.x)	xx (xx.x)	xx (xx.x)
....	xx (xx.x)	xx (xx.x)	xx (xx.x)	xx (xx.x)	xx (xx.x)

Notes: Subjects are counted at most once on each row. Subjects may be included on more than one row.

^a=Denominator for each % is the treatment group N.

^b=Denominator adjusted because gender-specific event for males: N=XX (FDP-CPD), N=XX (FDP-ACD) for Cohort 1; N=XX (FDP-CPD), N=XX (FDP-ACD) for Cohort 2; N=XX (810mL) for Cohort 3 [for applicable PTs].

^c=Denominator adjusted because gender-specific event for females: N=XX (FDP-CPD), N=XX (FDP-ACD) for Cohort 1; N=XX (FDP-CPD), N=XX (FDP-ACD) for Cohort 2; N=XX (810mL) for Cohort 3 [for applicable PTs].

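### The SAE row of SAP Table 2 and Tables 7.1-7.3 have no onset limit, so a donation-phase SAE in a later-infused Cohort 1-2 subject is counted under an FDP product column

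*SAP*

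**What the plan says.** The protocol synopsis (Objectives) bases the safety conclusion only on TEAEs and adds: "AEs occurring prior to treatment (e.g., AEs that occur during autologous plasma collection) will not be considered relevant to the study's objectives". Section 6.1 repeats the TEAE basis.

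Pre-infusion events still reach the AE data. Protocol 10.5.1 states: "The timeframe for the collection of AEs will begin at plasma collection". Other events between consent and first infusion are recorded as medical history, but "AEs associated with a study procedure (eg, blood or plasma donation) will be recorded in the AE section of the eCRF".

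SAP 4.5.3.1 opens its endpoint list with "The primary safety endpoints to be assessed are AEs, specifically" and names TEAEs, SAEs, SUSARs and deaths. Only the first carries a treatment-emergent qualifier. SAP section 2 describes SAEs as assessed in addition to TEAEs.

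In the SAP section 5 shells:
- Table 2 has two rows labelled treatment-emergent. The SAE row has no such label.
- Tables 3 to 6 are TEAE tables by title.
- Tables 7.1-7.3 are headed simply as SAEs, with "Number of subjects reporting serious adverse events" as the lead row. No title, row or programming note gives an onset limit.
- The Table 7 sort-order footnotes disagree. The Open version refers to a serious-event category and the Closed version to a treatment-emergent category.

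SAP 4.5.3 sends Tables 1.1 to 8.3, except 7.4-7.6, and Figures 1 and 2 to the DSMB.

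**The concern.** A programmer following the shells would count every recorded SAE in Table 2 and Tables 7.1-7.3, including one that occurred at a whole-blood or plasmapheresis session weeks before any product was given. In Cohorts 1 and 2 the columns are headed FDP-CPD and FDP-ACD, so harm from the donation would read as harm from the product. The protocol says such events do not bear on the study's objectives.

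No other planned summary table gives the treatment-emergent SAE count. Tables 5 and 6 grade severity, which protocol 10.4 distinguishes from seriousness. Listing 17 isolates pre-dose events, but the DSMB set named in SAP 4.5.3 contains no listings. Protocol 6.5 mentions SAEs, alongside TEAEs and the stopping rules, when it describes moving to the next cohort on DSMB recommendation, so these tables feed that review.

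Donation burden also varies by arm. Protocol Table 3 gives 1 whole-blood donation in Arm 1, 2 in Arm 3, and 3 to 4 plasmapheresis sessions in Cohort 3. An unrestricted SAE count therefore mixes product and dose with collection method and number of collections.

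**Working it through.** **The plan's own figure.** SAP Table 3 uses Clopper-Pearson limits: lower = Beta quantile(0.025; x, n-x+1), upper = Beta quantile(0.975; x+1, n-x). For n = 24 at 10% incidence, x = 2.4. The lower limit is Beta(0.025; 2.4, 22.6) = 1.6% and the upper is Beta(0.975; 3.4, 21.6) = 29.2%, a width of 27.6. This matches the SAP, and the other eight cells also reproduce to one decimal. The concern does not depend on this figure; it confirms the interval method.

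**Inputs.** There are 4 subjects per arm (SAP Table 1). Assume one procedure-related SAE at donation in one subject who is later infused, and no SAE after infusion.

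**Which tables pick up the event.**
- Protocol 10.5.1: it is recorded in the AE eCRF.
- SAP 4.2.2: the subject is in S1 once any volume is infused, and in S2 and S3 if those further conditions are met.
- Tables 3 to 6: excluded, because it is not treatment-emergent.
- Table 2 SAE row and Tables 7.1-7.3: included, because no onset limit is stated.

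**Effect on one Cohort 1 or 2 product column (n = 4).**
- As the shells are labelled: 1/4 = 25.0%. Lower limit 1 - 0.975^(1/4) = 0.6%; upper limit Beta(0.975; 2, 3) = 80.6%.
- Treatment-emergent only: 0/4 = 0%. Upper limit 1 - 0.025^(1/4) = 60.2%.

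**Effect elsewhere, same event.**
- Cohort 3 total column (n = 8): 1/8 = 12.5% (0.3-52.7) against 0/8 (0-36.9). No product is named in that column.
- Pooled over 24 subjects, for scale: 1/24 = 4.2% (0.1-21.1) against 0/24 (0-14.2).

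**Plausibility.** Protocol 5.6.1.2 and 5.6.1.3 list seizures for both collection methods, and tetany, arrhythmia and life-threatening allergic reaction for plasmapheresis. Section 10.2.2 gives convulsions without hospitalisation as an example of an event that may be serious. The documents give no rate, so no probability can be calculated.

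**The case against.** The best defence is that showing all SAEs may be deliberate. SAP section 2 sets SAEs beside TEAEs rather than inside them, and the protocol's rule governs what conclusions rest on, not what may be displayed. That stands as a reason to keep pre-infusion SAEs visible. It does not justify merging them, unlabelled, into a product column.

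It can also be said that a restriction was intended. The Closed footnote to Table 7 hints at it. But that footnote concerns sorting, the Open footnote differs, and nothing else states a limit.

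The reach is limited, and this stands in full. Tables 7.1-7.3 use S1 to S3, so the subject must have a procedure-related donation SAE and still be infused; a subject may instead be withdrawn for an SAE that raises a safety concern. Listing 18 gives onset date and relatedness for each SAE. Every SAE goes to the sponsor's safety office within 24 hours, and stopping rule 1 needs a product-related SAE. No hypothesis test or rate-based rule uses the percentage. The DSMB charter is not among the documents, so the board may receive onset information by another route.

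Three stronger readings are tempting but not supported:
- **Deaths are equally affected.** Table 2 has an unqualified row, "Fatal Adverse Events". But a subject who dies before infusion cannot be in S1, S2 or S3, and Tables 7.1-7.3 have no separate death row. Listing 19, which Table 2 cross-references, is treatment-emergent only. Such a death could appear only in the F1 or F2 version of Table 2.
- **TEAE rows in the F1 and F2 versions of Table 2 break SAP 4.2.2.** The rule is "Tables that are restricted to TEAEs will include the safety populations only". Table 2 is an overall AE table, which the same section assigns to all five populations. Its footnote states the denominator, and TEAE incidence in infused subjects is given in its S1 to S3 versions and in Table 3.
- **A wrong product SAE rate arises in Cohort 3.** The Table 2 and Table 7 shells for Cohort 3 show a total, masked A and B, or sequence. Randomisation is at most 48 hours before the first infusion, so a donation SAE would normally predate the assigned arm, but it is not placed under a product.

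**Conclusion.** The concern holds for SAEs. As written, the Table 2 SAE row and Tables 7.1-7.3 conflict with the protocol's stated basis for its safety conclusions. In Cohorts 1 and 2, one donation-phase SAE in a later-infused subject moves a product column from 0/4 to 1/4, that is from 0% to 25%, in a primary-endpoint table sent to the DSMB. This rests on 4 subjects per column, a single procedure-related event, and programming that follows the shell labels. Cohort 3 is affected only in its total, masked-arm or sequence counts. The frequency is unknown and the circumstances are narrow, so this should be fixed before tables are produced but is not a blocking fault.

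**What to change.** In SAP 4.5.3, Table 2 and Tables 7.1-7.3:
- Define a treatment-emergent SAE as one with onset at or after the start of infusion (the first infusion in Cohort 3), and report that as the product-attributed count.
- Show SAEs with onset before infusion in a separate row or column labelled as such. Keep it in the DSMB tables, because Listing 17 is outside the set named in SAP 4.5.3.
- Give the Open and Closed versions of Table 7 the same footnote.

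The cost is SAP wording and minor shell edits. Tables 3 to 6 and Listings 13 and 17 already require events to be classified as before or after the start of infusion, so no new data are needed.

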#### **Criteria for Evaluation:**

**Primary Endpoints**. The primary endpoints to be assessed are AEs, specifically TEAEs; SAEs; Suspected, Unexpected, Serious Adverse Reactions (SUSARs); and death.

**Secondary Endpoints.** In Cohort 3, the change in pre- and post-infusion measurement of the endpoints listed below will be compared:

- PT, INR, aPTT, Factors I, II, V, VII, VIII, IX, X, XI, D-Dimer, von Willebrand factor activity, Protein S activity, Protein C activity, PF 1+2, TAT, Antithrombin III, Alpha-2 Antiplasmin, and C3a des Arg compared to pre-infusion values after 3 unit infusion of FDP compared to 3 unit infusion of FFP; and
- Hematology, urinalysis, vital signs, DAT and chemistry values compared to pre-infusion values after 3 unit infusion of FDP compared to 3 unit infusion of FFP.

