#### 6.4.2. Secondary Endpoints

The following secondary endpoints will only be evaluated in Cohort 3 subjects:

• Change in pre- and post-infusion values for Prothrombin Time and International Normalized Ratio (PT/INR), aPTT, Factors I, II, V, VII, VIII, IX, X, XI, D-DIMER, von Willebrand Factor activity, Protein S activity, Protein C activity, Prothrombin

Fragments 1+2 (PF 1+2), Thrombin/Antithrombin (TAT), Antithrombin III (AT-III), Alpha-2 antiplasmin, and C3a des Arg activity compared to pre-infusion values after infusion of 3 units of FDP compared to 3 units of FFP; and

• Determine if the changes in specific hematology, urinalysis, vital signs, DAT, and chemistry values are similar within clinically meaningful levels after infusion of either 3 units of autologous FDP or FFP.

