4.5.4.1 Secondary Endpoints

The secondary endpoints for this study and associated time points for analysis are listed in Table 5.

Table 5. Secondary Safety Endpoints and Scheduled Measurements of Secondary Endpoints*

Safety Endpoints	Pre-Infusion	Post-Infusion			
		0.5 Hours	4 Hours	24 Hours	28 Days
Vital Signs:					
Blood Pressure	X	X	X		
Heart Rate	X	X	X		
Respiration Rate	X	X	X		
Temperature	X	X	X		
Urinalysis:					
Glucose	X	X	X		
Ketones	X	X	X		
Protein	X	X	X		
Blood	X	X	X		
Leukocyte Esterase	X	X	X		
Nitrite	X	X	X		
Bilirubin	X	X	X		
Hematology:					
Hematocrit	X	X	X	X	
Hemoglobin	X	X	X	X	
Platelet Count	X	X	X	X	
RBC Count	X	X	X	X	
WBC Count	X	X	X	X	
Direct Antiglobulin Test (DAT) (IgG and C3)	X				
Clinical Chemistry:					
ALP	X	X	X		
ALT	X	X	X		
AST	X	X	X		
Ionized Calcium	X	X			
Total Magnesium	X	X			
pH	X	X			
Electrolytes (Calcium, Chloride, Potassium, Sodium, Lactic Acid, and Bicarbonate)	X	X	X		
Glucose	X	X	X		
Total Bilirubin	X	X	X		
Total Protein	X	X	X		
BUN	X	X	X		
Creatinine	X	X	X		
Coagulation Tests:					
PT	X	X	X	X	X
INR	X	X	X	X	X
aPTT	X	X	X	X	X
D-dimer	X	X	X	X	
Cohort 3 safety analyses will also include measurements taken at each Infusion Visit at the following post-infusion time points.					
Factor I	X	X	X		
Factor II	X	X	X		
Factor V	X	X	X		

Safety Endpoints	Pre-Infusion	Post-Infusion			
		0.5 Hours	4 Hours	24 Hours	28 Days
Factor VII	X	X	X		
Factor VIII	X	X	X		
Factor IX	X	X	X		
Factor X	X	X	X		
Factor XI	X	X	X		
von Willebrand Factor Activity	X	X	X		
Protein C Activity	X	X	X		
Protein S Activity	X	X	X		
PF 1+2	X	X			
TAT	X	X			
Antithrombin III	X	X			
Alpha-2 Antiplasmin	X	X			
C3a des Arg	X	X			

* Grayed cells mean that the time point either was not measured or will not be used in the analysis.

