The title for Cohort 3 for the second infusion is shown below:

Table XX.XX Measures (Units) Change from Baseline Over Time Since Treatment Emergent Change
XX Measures (Units) Change from Baseline Over Time Since Treatment Emergent Change – Cohort 3 (810 mL) – Infusion #2
Safety Population – S3 (N=XX)
FDP-1
Phase I

Note: ^a=Denominator for each % is the treatment group N at each individual time point

76

Program Path:

Data source: ADVS, ADLB Cross Reference: Listing 10-12, Listing 20-23, Listing 26-27

Data extract date:

Table 10.1. – Table 10.36. XX Measures (Percentage) Over Time Since Treatment Emergent Change
XX Measures (Percentage) Over Time Since Treatment Emergent Change – Cohort 1 (270 mL)

Safety Population – S3 (N=XX)

FDP-1

Phase I

Treatment	Pre-Infusion		Post-Infusion			
			30 min		4 hrs	
	FDP-CPD	FDP-ACD	FDP-CPD	FDP-ACD	FDP-CPD	FDP-ACD
n ^a	xx	xx	xx	xx	xx	xx
Negative	xx (x.x)	xx (x.x)	xx (x.x)	xx (x.x)	xx (x.x)	xx (x.x)
Positive	xx (x.x)	xx (x.x)	xx (x.x)	xx (x.x)	xx (x.x)	xx (x.x)

^aNumber of subjects with non-missing data, used as the denominator

Programming Note: This table has been restricted to the time points pre-infusion, 30 minutes and 4 hours post infusion at the request of the investigator. This table will be produced for the following endpoints where data are available:

- Urinalysis:
 - Glucose (Table 10.1)
 - Ketones (Table 10.2)
 - Protein (Table 10.3)
 - Blood (Table 10.4)
 - Leukocyte esterase (Table 10.5)
 - Nitrite (Table 10.6)
 - Bilirubin (Table 10.7)
- Direct Antiglobulin Test (DAT):
 - Immunoglobulin G (Table 10.8)
 - Complement C3 (Table 10.9)

Programming Note: This table will be repeated for Cohort 2 (Table 10.10-10.18) as follows:

- Urinalysis:

Note: a=Denominator for each % is the treatment group N.

Program Path:

Data source:ADLB Cross Reference: Listing 24-25, Listing 28

Data extract date:

- Glucose (Table 10.10)
- Ketones (Table 10.11)
- Protein (Table 10.12)
- Blood (Table 10.13)
- Leukocyte esterase (Table 10.14)
- Nitrite (Table 10.15)
- Bilirubin (Table 10.16)
- Direct Antiglobulin Test (DAT):
 - Immunoglobulin G (Table 10.17)
 - Complement C3 (Table 10.18)

The title for Cohort 2 are listed below:

Table XX. Measures (Percentage) Over Time Since Treatment Emergent Change
XX Measures (Percentage) Over Time Since Treatment Emergent Change – Cohort 2 (540 mL)
Safety Population – S3 (N=XX)
FDP-1
Phase I

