Programming Note: This table will also be repeated for Cohort 3 (Table 10.19-10.27) for the first infusion:

- Urinalysis:
 - Glucose (Table 10.19)
 - Ketones (Table 10.20)
 - Protein (Table 10.21)
 - Blood (Table 10.22)
 - Leukocyte esterase (Table 10.23)
 - Nitrite (Table 10.24)
 - Bilirubin (Table 10.25)
- Direct Antiglobulin Test (DAT):
 - Immunoglobulin G (Table 10.26)
 - Complement C3 (Table 10.27)

Note: a=Denominator for each % is the treatment group N.

Programming Note: This table will also be repeated for Cohort 3 (Table 10.28-10.36) for the second infusion:

- Urinalysis:
 - Glucose (Table 10.28)
 - Ketones (Table 10.29)
 - Protein (Table 10.30)
 - Blood (Table 10.31)
 - Leukocyte esterase (Table 10.32)
 - Nitrite (Table 10.33)
 - Bilirubin (Table 10.34)
- Direct Antiglobulin Test (DAT):
 - Immunoglobulin G (Table 10.35)
 - Complement C3 (Table 10.36)

Programming Note: For Cohort 3, the treatment arms will be unmasked for final data analysis once the study has been unblinded. The titles for Cohort 3 are shown below:

Table XX. Measures (Percentage) Over Time Since Treatment Emergent Change
XX Measures (Percentage) Over Time Since Treatment Emergent Change – Cohort 3 (810 mL) – Infusion #1
Safety Population – S3 (N=XX)
FDP-1
Phase I

Table XX. Measures (Percentage) Over Time Since Treatment Emergent Change
XX Measures (Percentage) Over Time Since Treatment Emergent Change – Cohort 3 (810 mL) – Infusion #2
Safety Population – S3 (N=XX)
FDP-1
Phase I

Note: a=Denominator for each % is the treatment group N.

Table 11.1. – Table 11.34. Shift Table Summary of Number of Subjects with Absolute Laboratory Values for XX Measure (Unit) Pre-Infusion vs. Max Post-Infusion

**Absolute Lab Values for XX Measure (Unit) Pre-Infusion vs. Max Post- Infusion – Cohort 1 (270 mL)
 Safety Population – S3 (N=XX)**

**FDP-1
 Phase I**

Treatment	Treatment Emergent High		
	N	n	%
FDP-CPD			
FDP-ACD			

Programming Note: This table will be produced for the following endpoints for Cohort 1 (Table 11.1-11.4):

- Coagulation Factor Tests:
 - PT (Table 11.1)
 - INR (Table 11.2)
 - aPTT (Table 11.3)
 - D-Dimer (ug/mL FEU) (Table 11.4)

Programming Note: This table will be produced for the following endpoints for Cohort 2 (Table 11.5-11.8):

- Coagulation Factor Tests:
 - PT (Table 11.5)
 - INR (Table 11.6)
 - aPTT (Table 11.7)
 - D-Dimer (ug/mL FEU) (Table 11.8)

The titles for Cohort 2 is listed below:

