 - Total Bilirubin (mg/dL) (Table 12.19)
 - Total Protein (g/dL) (Table 12.20)

- BUN (mg/dL) (Table 12.21)
- Creatinine (mg/dL) (Table 12.22)
- Coagulation Factor Tests:
 - PT (sec) (Table 12.23)
 - INR (Table 12.24)
 - aPTT (sec) (Table 12.25)
 - Factor I (mg/dL) (Table 12.26)
 - Factor II (% Normal) (Table 12.27)
 - Factor V (% Normal) (Table 12.28)
 - Factor VII (% Normal) (Table 12.29)
 - Factor VIII (% Normal) (Table 12.30)
 - Factor IX (% Normal) (Table 12.31)
 - Factor X (% Normal) (Table 12.32)
 - Factor XI (% Normal) (Table 12.33)
 - von Willebrand Factor Activity (%) (Table 12.34)
 - Protein C (Factor XIV Activity) (% Normal) (Table 12.35)
 - Protein S (% Normal) (Table 12.36)
 - Antithrombin III (% Normal) (Table 12.37)
 - Alpha-2 Antiplasmin (% Normal) (Table 12.38)

Table 13.1-Table 13.2. Treatment Group (Sequence) by Period Descriptive Statistics for Number of Subjects with XX Measures (Percentage)

Treatment Group (Sequence) by Period Descriptive Statistics for Number of Subjects with XX Measures (Percentage) – Cohort 3 (810 mL)

Safety Population – S3 (N=XX)

FDP-1

Phase I

		Period 1	Period 2
FDP-ACD X FFP (Sequence)		Pre-Infusion	Pre-Infusion
	N	xx	xx
	Negative	xx(x.x)	xx(x.x)
	Positive	xx(x.x)	xx(x.x)
FFP X FDP-ACD (Sequence)		Pre-Infusion	Pre-Infusion
	N	xx	xx
	Negative	xx(x.x)	xx(x.x)
	Positive	xx(x.x)	xx(x.x)
Total		Pre-Infusion	Pre-Infusion
	N	xx	xx
	Negative	xx(x.x)	xx(x.x)
	Positive	xx(x.x)	xx(x.x)

Programming Note: This table will be produced for the following endpoints where data is available:

- Direct Antiglobulin Test (DAT):
 - Immunoglobulin G (Table 13.1)
 - Complement C3 (Table 13.2)

For Cohort 3, the treatment arms will be unmasked for final data analysis once the study has been unblinded.

Note: Denominator for each % is the time point column N.

87

Program Path:

Data source: ADLB Cross Reference: Listing 28

Data extract date:

**Table 14. Summary of Subject Exposure to Study Drug
 Safety Population – S1 (N=XX)
 FDP-1
 Phase I**

		FDP- CPD (270 mL) N=XX	FDP- ACD (270 mL) N=XX	FDP- CPD (540 mL) N=XX	FDP- ACD (540 mL) N=XX	FDP-ACD X FFP (810 mL) N=XX	FFP X FDP-ACD (810 mL) N=XX	Overall N=XX
Total Amount Administered (mL) – Infusion #1								
	n ^a	XX	XX	XX	XX	XX	XX	XX
	Mean	XX.X	XX.X	XX.X	XX.X	XX.X	XX.X	XX.X
	SD	XX.X	XX.X	XX.X	XX.X	XX.X	XX.X	XX.X
	Median	XX.X	XX.X	XX.X	XX.X	XX.X	XX.X	XX.X
	Q1, Q3	XX,XX	XX,XX	XX,XX	XX,XX	XX,XX	XX,XX	XX,XX
	Min, Max	XX,XX	XX,XX	XX,XX	XX,XX	XX,XX	XX,XX	XX,XX

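### No SAP summary table shows the 24-hour DAT that Protocol Table 15 plans for Cohort 3, where DAT is a named secondary endpoint

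*SAP*

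**What the plan says.** The protocol synopsis (Criteria for Evaluation) lists among the Cohort 3 secondary endpoints "Hematology, urinalysis, vital signs, DAT and chemistry values compared to pre-infusion values after 3 unit infusion of FDP", set against the same dose of FFP. Protocol 6.4.2 names DAT again under the statement "The following secondary endpoints will only be evaluated in Cohort 3 subjects".

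Protocol 11.1.2.1 gives Table 15 as the list of secondary endpoints with their analysis time points. Its DAT row is marked at pre-infusion and at 24 hours. The collection schedules in Protocol Tables 9 and 11 agree that the 24-hour sample is drawn.

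The SAP departs from this in three places:

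- **SAP Table 5** (section 4.5.4.1) marks DAT at pre-infusion only. Its footnote says "Grayed cells mean that the time point either was not measured or will not be used in the analysis".
- **SAP Table 10** (section 5) covers urinalysis and DAT together. Its programming note says "This table has been restricted to the time points pre-infusion, 30 minutes and 4 hours post infusion at the request of the investigator", with no exception for DAT.
- **SAP Table 13** (section 5), the by-sequence and by-period DAT table, has one pre-infusion column for each period and nothing else.

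For PT, INR and aPTT, SAP Table 5 does mark 24 hours. The notes to SAP Tables 9 and 12, however, keep the printed 24-hour column for the hematology variables only.

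**The concern.** The endpoint is DAT after infusion set against DAT before infusion, for FDP and for FFP. A table of pre-infusion results cannot show that. The 24-hour reading is the only post-infusion time point that Protocol Table 15 marks for DAT, and it is the one the SAP leaves out. Because a positive DAT excludes a subject (Protocol 7.5), the pre-infusion results before Infusion #1 should be negative almost by design. The information lies in who converts afterwards.

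At stake is one planned descriptive comparison in a first-in-human safety study in which post-infusion hemolysis is a stopping rule. If the SAP is programmed as written, the study report will have DAT tables that do not contain the result they were planned to show.

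**Working it through.** No sample size, power or error rate is involved. The check sets the DAT time points side by side and counts what is left out.

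| Place | Pre-infusion | 30 min | 4 h | 24 h |
|---|---|---|---|---|
| Protocol Tables 9 and 11 (collection) | yes | no | no | yes |
| Protocol 8.2.2 (infusion-day test list) | – | yes | yes | – |
| Protocol Table 15 (analysis) | yes | no | no | yes |
| SAP Table 5 (analysis) | yes | no | no | no |
| SAP Tables 10.26-10.27, 10.35-10.36 | yes | yes | yes | no |
| SAP Tables 13.1-13.2 | yes, each period | no | no | no |

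**Is the SAP gap a stray mark?** Probably not. The hematology rows next to DAT in SAP Table 5 carry their 24-hour marks, and Table 13 is also pre-infusion only. SAP Tables 9, 11 and 12 and Figures 3 and 4 do not include DAT, so no other summary output fills the gap.

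**Shells affected.** 2 (Infusion #1 versions of Table 10) + 2 (Infusion #2 versions) + 2 (Table 13) = 6 Cohort 3 DAT shells. Shells with a 24-hour column: 0.

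**Draws affected.** Cohort 3 plans 8 completers (SAP 3.4) with 2 infusions each. 24-hour draws: 8 × 2 = 16. Each is read for IgG and for C3: 16 × 2 = 32 results.

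**What the shells would hold.** The protocol conflicts with itself on the 30-minute and 4-hour draws, so there are two cases.

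- If Protocol Tables 9 and 11 hold, the 30-minute and 4-hour DAT columns of SAP Table 10 have nothing to show. The only reading in the six shells taken after any product is the one before Infusion #2, about 14 days after Infusion #1. Nothing follows Infusion #2.
- If Protocol 8.2.2 holds, Table 10 shows DAT at 30 minutes and 4 hours, but still not at 24 hours.

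The 24-hour result is absent in both cases.

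**PT, INR and aPTT (minor).** The Cohort 3 change-from-baseline shells are 9.88-9.90 (3), 9.131-9.133 (3) and 12.23-12.25 (3), so 3 + 3 + 3 = 9. SAP Table 5 marks 24 hours for all three tests. The printed shells of Tables 9 and 12 have the column, and the notes withhold it from these tests.

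**The case against.** The strongest reply is that this was a choice. SAP Table 5, its footnote, Table 13 and the investigator's request behind the Table 10 note are consistent with one another. That may be so. The note gives no reason, however, and Protocol 11.6 asks for departures from the protocol's statistical plan to be described in an amendment to the protocol and the SAP. I cannot tell from the text whether that was done. This is why the fix offers description as an alternative.

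The protocol's statistical methods also allow data to be shown as listings, tables or figures, and Listing 30 gives DAT by subject and visit. That stands as far as availability goes. Protocol Table 15, though, sets time points for analysis, and a by-subject listing is not the planned descriptive comparison.

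Protocol 11.1.2.1 and SAP 4.5.4 limit the change summaries to cases where they are appropriate and define change as a subtraction, which does not suit a negative/positive test. It is true that no difference can be computed. SAP Table 10 already has the right format, counts of negative and positive at each time point. It only needs the column.

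The effect is small: the study is descriptive, with 8 subjects, and no hypothesis is tested. I accept that.

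Some stronger readings are tempting but are not supported:

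- *That the 24-hour DAT data are lost.* They are in Listing 30, and a conversion judged an adverse event would also reach the AE tables.
- *That no post-infusion DAT can appear in any table.* That depends on which protocol schedule holds.
- *That missing 28-day PT, INR and aPTT columns weaken the product comparison.* Cohort 3 has a single 28-day visit, after both products (Protocol 8.3.4).
- *That D-dimer is omitted in the same way.* The SAP assigns D-dimer to shift tables for secondary objective 2.

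**Conclusion.** The point holds for DAT in Cohort 3. The SAP drops the 24-hour analysis that Protocol Table 15 plans for a named secondary endpoint, and following the SAP exactly yields no 24-hour DAT summary. In size, 16 planned draws (32 IgG and C3 results) enter 0 of 6 shells. This assumes 8 completers with both infusions and both 24-hour visits done. It does not depend on which protocol passage governs the 30-minute and 4-hour draws. It should be corrected before the SAP is applied, but it does not threaten the trial's conclusions.

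The PT, INR and aPTT mismatch is real but minor. The Table 11 shift tables and Figures 4.1-4.3 state no 4-hour limit and may carry the later values, and Listings 28-29 hold them.

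The wrong listing references noted under the fix are clerical. They have no bearing on whether DAT is summarised.

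**What to change.** 1. Restore the 24-hour mark for DAT in SAP Table 5.
2. Exempt DAT from the time-point restriction in the note to SAP Table 10.
3. Add a 24-hour column, with counts of subjects going from negative to positive, to Tables 10.26-10.27, 10.35-10.36 and 13.1-13.2.
4. If the omission was intended, describe it as Protocol 11.6 requires instead of making changes 1 to 3.
5. Reconcile Protocol 8.2.2 with Protocol Tables 9 and 11 before deciding whether the 30-minute and 4-hour DAT columns stay.
6. Minor: extend the hematology exception in the notes to SAP Tables 9 and 12 to PT, INR and aPTT at 24 hours for Cohort 3 (nine shells, column already printed).

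Editorial note: the source lines of Table 13 ("Data source: ADLB Cross Reference: Listing 28") and Table 10 ("Cross Reference: Listing 24-25, Listing 28") point to a coagulation listing, whereas DAT is Listing 30. Tables 9 and 11 cite Listings 26-27, which are urinalysis, whereas coagulation is Listings 28-29.

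The cost is one mark, one column in six shells, a phrase in three programming notes, corrected source lines and one protocol reconciliation. No new data are needed, because the 24-hour samples are already scheduled and listed.
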